6.11.1 Primary Analysis

The primary analysis will be based on the FAS and CAS. Peak FEV_1 and AUC_{0-12h} FEV₁ measured after dosing on Day 3 will be analysed.

Log_e (Max FEV₁) and log_e (AUC_{0-12h} FEV₁/12) will be compared between the three study treatments using ANCOVA models with fixed factors for treatment, period and patient, and using the log_e baseline FEV₁ of the treatment period (pre-first dose in a treatment period) as a covariate. FEV₁ will be analysed using multiplicative models, and the result then transformed back to the linear scale giving treatment differences as ratios of geometric means. Primarily the combination tiotropium + RPL554 will be compared to tiotropium + Placebo RPL554 for each of the two doses of RPL554. Results of the comparisons will be expressed as the mean geometric ratio with 95% confidence intervals and associated, 2-sided, p-value.

Derived FEV₁ data will be summarised and listed.

Example SAS code for Peak FEV₁ analysis is as follows:

```
PROC GLM DATA=dataset;
CLASS TREATMENT PATIENT PERIOD;
MODEL LOGE(MAX 4HRS POSTDOSE VALUE) = TREATMENT PATIENT PERIOD
LOGE(BASELINE);
LSMEANS TREATMENT / DIFF PDIFF CL;
RUN;
```

Example SAS code for $AUC_{0-12h} FEV_1$ analysis is as follows:

```
PROC GLM DATA=dataset;
CLASS TREATMENT PATIENT PERIOD;
MODEL LOGE(AUC/12) = TREATMENT PATIENT PERIOD LOGE(BASELINE);
LSMEANS TREATMENT / DIFF PDIFF CL;
RUN;
```

6.12 Secondary Endpoints

The following endpoints will be analysed based on the FAS:

AUC_{0-4h} FEV₁ after morning dosing on Day 1, Day 2 and Day 3

Log_e (AUC_{0-4h} FEV₁/4)

Peak FEV₁ (measured in first 4 hours after dosing) and AUC_{0-12h} FEV₁ Day 1

Peak effect and average effect will be \log_e transformed in order to perform a multiplicative ANCOVA as follows:

Log_e (Max FEV₁)

Log_e (AUC_{0-12h} FEV₁/12)

Onset of action

Time to onset of action will be determined for each patient on Day 1 of each treatment period. The scheduled timepoint at which $\geq 10\%$ increase from baseline was achieved and the scheduled timepoint before that will be interpolated to determine the time relative to dosing at which 10% increase occurred for that patient on that treatment day. Subjects who do not achieve a 10% increase from baseline by 120 minutes (2 hours postdose) on Day 1 will be censored.

The following formulae will be used to derive the time to onset:

Time to Onset = Time A + (FEV₁ target - FEV₁ A)/ (FEV₁ B - FEV₁ A) * (Time B - Time A)

Where:

- Time A is the scheduled timepoint before 10% increase is met
- Time B is the scheduled timepoint at which 10% increase is met
- FEV₁ target is the FEV₁ value corresponding to a 10% increase or, if FEV₁ is expressed as percentage increases from baseline, it is the value 10 itself
- FEV_1 A is the maximum FEV_1 measurement at the timepoint before 10% increase is met
- FEV₁ B is the maximum FEV₁ measurement at the timepoint at which 10% increase is met

RV, FRC, sG_{aw} and R_{aw} at 1.25 hours after dosing on Day 2

Ability to adequately perform whole body plethysmography will be conducted at screening. Whole body plethysmography assessments will be conducted at pre-dose Day 1, pre-dose and 1.25 hours post-dose on Day 2 of each treatment period. Patients will be placed on a body box for plethysmographic determination of lung volumes, to include RV, FRC and total lung capacity (TLC). Additionally,

measurements will be made of airway conductance (sG_{aw}) and airway resistance (R_{aw}).

Plethysmographic endpoints will be calculated on Day 2, at both pre-dose and 1.25 hours post dose of each treatment period. The change from pre-dose Day 1 will be calculated for RV, FRC, sG_{aw} and R_{aw} at 1.25 hours post-dose on Day 2 of each treatment period.

AUC, C_{max}, t_{max} and half-life

RPL554 steady state pharmacokinetics (AUC, maximum observed concentration (C_{max}) , time to maximum concentration (t_{max}) and half-life) will be determined. Analysis of PK data is detailed in section 6.16.

Rescue Medication

The use of rescue medication during the study will documented. Short acting bronchodilators (e.g. salbutamol, ipratropium or Combivent) may be used as rescue medication. Salbutamol should be considered the primary rescue medication and ipratropium secondary. The time to the first rescue medication use is defined as the duration from the date of first dose of study treatment to the date of the first administration of a rescue medication for each study period calculated in hours. Subjects who do not use rescue medication will be right-censored at the date of the last timepoint of the last treatment day of each study period.

Tolerability and Safety

Assessment of safety and tolerability of twice daily nebulised doses of RPL554 in addition to tiotropium is detailed in section 6.17.

6.12.1 Secondary Analysis

Continuous variables will be compared between the three study treatments using analysis of covariance (ANCOVA) models with fixed factors for treatment, period and patient, and using the log_e baseline measurement of the treatment day (pre-first dose in a treatment period) as a covariate. The analysis uses multiplicative models.

The combination of tiotropium + RPL554 will be compared to tiotropium alone for each of the two doses of RPL554. Results of the comparisons will be expressed as the mean geometric ratio with 95% confidence intervals and associated, 2-sided, p-value.

 AUC_{0-4h} FEV₁ after morning dosing will be determined separately for Day 1, Day 2 and Day 3 and analysed as above, as average effect ($AUC_{0-4h}/4$ FEV₁). Median time to onset of action for each study treatment will be calculated. The median time to onset across all patients will only be reported if at least 50% of patients achieve a 10% increase from baseline in FEV1 from pre-first dose within 120 minutes on Day 1. 95% CI of the median time to onset will also be presented. Kaplan-Meier plot illustrating time to onset will also be constructed. Where possible, the median time to onset of action data will be compared using a Wilcoxon signed rank test. P-values will be generated for comparisons of the median time to onset of the two tiotropium + RPL554 doses against tiotropium + Placebo.

 Log_e transformed Plethysmographic endpoints will be compared in the same way as FEV₁. The log_e baseline of the treatment day (pre-first dose in a treatment period) will be used as covariate in these models. Results of the comparisons will be back

transformed and expressed as the mean geometric ratio with 95% confidence intervals and associated, 2-sided, p-value.

All plethysmography data will be listed and summarised where applicable. A histogram of change from baseline (pre-dose day 2 to pre-dose day 1) and (post-dose day 2 to pre-dose day 1) mean plethysmography data will be presented for actual values and percent predicted values of RV, FRC and actual values for sGaw and R_{aw} for each study treatment. All treatments will be presented on the same figure.

The use of rescue medication during the study timepoints will be summarised by treatment, as the number and percentage of patients who used rescue medication, and, if appropriate, a Kaplan-Meier plot illustrating time to first use of rescue constructed. Rescue medication data will also be listed.

6.13 Exploratory Endpoints

The following endpoint will be analysed based on the FAS:

- Pre-dose FEV₁ on Day 3

6.13.1 Exploratory Analysis

Log_e (pre-dose FEV₁) on Day 3 will be compared between the three study treatments using analysis of covariance (ANCOVA) models with fixed factors for treatment, period and patient, and using the baseline measurement of the treatment day (pre-first dose in a treatment period) as a covariate. The analysis uses multiplicative models and the result will be transformed back to the linear scale giving treatment differences as ratios of geometric means.

The combination of tiotropium + RPL554 will be compared to Placebo tiotropium + RPL554 for each of the two doses of RPL554. Results of the comparisons will be expressed as the mean geometric ratio with 95% confidence intervals and associated, 2-sided, p-value.

6.14 Summary of AUC Data

Changes from baseline in AUC parameters will be derived using the following definitions for baseline:

- AUC_{0-4h}: 4 * pre-dose treatment day 1 value
- AUC_{0-12h}: 12 * pre-dose treatment day 1 value
- AUC_{0-24h}: 24 * pre-dose treatment day 1 value

6.15 Multiplicity

For the primary endpoints analyses, a closed test procedure will be used to maintain the overall type 1 error rate starting with the highest dose of RPL554. The method is illustrated in Figure 1 below.

FIGURE 1: CLOSED TESTING PROCEDURE

For the RPL554 6mg dose compared to RPL554 Placebo for each of peak and AUC $FEV_{1,}$ a significant result will be required for both variables to proceed to testing the lower dose.

If H_1 and H_2 are rejected, then analysis of the primary endpoints will stop here. However, if both H_1 and H_2 are accepted then the above closed test procedures will be repeated for the lower dose of RPL554 compared to placebo RPL554. If either H_1 or H_2 are accepted, testing will continue for the hypothesis that was accepted for the lower dose of RPL554 compared to placebo RPL554.

The adjusted p-value of the relevant endpoint from above, will be used to assess significance.

All secondary endpoints and the supportive analyses will be considered as descriptive evidence of efficacy and will be analysed without any procedures to account for multiple comparisons.

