10.3 Study Endpoints

10.3.1 Primary Endpoints

Peak FEV_1 (measured in first 4 hours after dosing) and AUC_{0-12h} FEV_1 . These will be measured after dosing on Day 3.

The primary comparisons are RPL554 6mg + tiotropium vs RPL554 placebo + tiotropium, followed by RPL554 1.5 mg + tiotropium vs RPL554 placebo + tiotropium.

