6.11 Primary Endpoints

Peak FEV₁ (measured in first 4 hours after dosing) and AUC_{0-12h} FEV₁. These will be measured after dosing on Day 3

The peak effect on FEV_1 during these time intervals will be computed as the maximum value within the 4 hours after dosing minus the pre-dose Day 1 baseline value.

The average effect will be calculated as the AUC divided by the length of the time interval of interest. The AUC parameters will be calculated using the linear trapezoidal rule.

Pre-dose treatment day 1 value for each treatment period will be used as the baseline value.

Changes from baseline in AUC average effect parameters will be derived by deducting the pre-dose treatment day 1 value from the average effect.

Peak effect and average effect will be log_e transformed in order to perform a multiplicative (Analysis of Covariance) ANCOVA as follows:

Log_e (Max FEV₁)

 Log_e (AUC_{0-12h} FEV₁ /12)

Spirometry performed within 8 hours after the use of a rescue bronchodilator (salbutamol) will not be utilized in calculations of peak or AUC FEV_1 .

Observed FEV_1 data will be summarised as actual and change from baseline using descriptive statistics over time.

Hypothesis to be tested:

 H_0 = tiotropium + RPL554 in patients with COPD has the same effect on FEV₁(first 4 hours)/ AUC_{0-12h} FEV₁ as tiotropium + Placebo

The primary comparisons are tiotropium + RPL554 6mg vs tiotropium + RPL554 placebo, followed by tiotropium + RPL554 1.5mg vs tiotropium + RPL554 placebo.

All hypothesis testing will be done using two-sided alternative hypotheses. P-values less than 5% will be considered statistically significant.

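### SAP 6.15 gives conflicting rules for when the 1.5 mg dose may be tested on the two primary endpoints

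*SAP*

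**What the plan says.** There are two primary endpoints on Day 3 (peak FEV1 over 4 hours and AUC0-12h FEV1) and two RPL554 doses compared with placebo, so there are four primary tests. SAP 6.11 and Protocol 10.3.1 both put 6 mg first, "followed by tiotropium + RPL554 1.5mg vs tiotropium + RPL554 placebo" in the SAP's wording. The Protocol synopsis also calls for a closed procedure that begins at the top dose. SAP 6.1 sets a two-sided 5% overall level and states that the null is always equivalence of treatments.

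SAP 6.15 promises to hold the overall type 1 error and gives these instructions:

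- **A (gate).** At 6 mg, "a significant result will be required for both variables to proceed to testing the lower dose".
- **B.** "If H_1 and H_2 are rejected, then analysis of the primary endpoints will stop here".
- **C.** "However, if both H_1 and H_2 are accepted then the above closed test procedures will be repeated for the lower dose of RPL554".
- **D.** "If either H_1 or H_2 are accepted, testing will continue for the hypothesis that was accepted"; this too refers to the lower dose.
- **E.** "The adjusted p-value of the relevant endpoint from above, will be used to assess significance".

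The method is said to be shown in Figure 1, whose content was not available for this review. The readable text does not define H_1, H_2, the within-dose intersection test or the adjustment. Figure 1 may do so, and its absence here is not held against the plan.

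**The concern.** Sentence A and sentences B to D answer the same question, namely what to do at 1.5 mg given the 6 mg result, and they answer it differently. This is the decision rule for both primary endpoints. Two analysts following the same section could reach opposite confirmatory conclusions on 1.5 mg, including in the outcome the trial hopes for, where 6 mg succeeds on both endpoints. If the rule is settled only after the results are known, the promise of overall error control loses its basis. What is at stake is limited to the confirmatory claim for 1.5 mg. SAP 6.11.1 still reports every comparison: "Results of the comparisons will be expressed as the mean geometric ratio with 95% confidence intervals and associated, 2-sided, p-value".

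**Working it through.** **1. The plan's own figure.** On the log scale the standard error of a pairwise contrast is s·√(2/n). With s = 0.06 and n = 24 this is 0.06 × √(2/24) = 0.01732. The stated difference is ln(1.051) = 0.0497, or 2.87 standard errors. A noncentral t with 43–44 df gives 80.2–80.3% power, so the SAP's 80% is reproduced. The concern does not touch the sample size.

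**2. The rules side by side.**

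| 6 mg result | A (gate) | B–D, H_1/H_2 as nulls | B–D, H_1/H_2 as alternatives |
|---|---|---|---|
| Both significant | test 1.5 mg | stop | test 1.5 mg |
| Exactly one significant | stop | test 1.5 mg on the endpoint that failed | test 1.5 mg on the endpoint that succeeded |
| Neither significant | stop | test 1.5 mg on both | stop |

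Read as nulls, B–D disagree with the gate in 3 of 3 outcomes. Read as alternatives, or with accepted and rejected swapped, they disagree in 1 of 3. That remaining conflict comes from D.

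**3. Does sentence E rescue it?** Suppose the 6 mg adjusted p-value carries down, so that the 1.5 mg value is max(p at 6 mg, p at 1.5 mg). On the null reading an endpoint reaches 1.5 mg only when its 6 mg p-value exceeds 0.05, so the maximum also exceeds 0.05. Error is then controlled, but 1.5 mg can never be declared.

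**4. Size, by simulation** (1,000,000 replicates per scenario). Four correlated z-statistics were drawn and tested at two-sided 5%.

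- The correlation between the two dose contrasts is 0.5. They share the placebo mean: covariance s²/n over variance 2s²/n.
- The peak–AUC correlation is an assumption, 0.5 to 0.9.
- The within-dose test is an assumption, Holm or Hochberg.
- 80% power corresponds to a z-shift of 1.96 + 0.84 = 2.80.
- In the literal B–D rule, if both endpoints are accepted the closed test is repeated at 1.5 mg. If one is accepted, that endpoint is tested at unadjusted 5%.

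*Family-wise error, no effect anywhere:*

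| Within-dose test, peak–AUC correlation | Gate | B–D as nulls, no carry-down |
|---|---|---|
| Hochberg, 0.5 | 4.82% | 8.80% |
| Hochberg, 0.9 | 4.12% | 7.57% |
| Holm, 0.5 | 4.66% | 8.55% |
| Holm, 0.9 | 3.65% | 6.70% |

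With carry-down, B–D as nulls gives 3.7–4.8%, and 1.5 mg is declared in 0 of 1,000,000 trials, as step 3 requires.

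The within-dose test matters in its own right. In a separate run of 400,000 draws with each endpoint at unadjusted 5%, the gate gave 7.0–9.0% and B–D as nulls 12.6–16.0%.

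*80% power on all four comparisons:* both 6 mg tests reject in 68–75% of trials. 1.5 mg is declared on at least one endpoint in 62–65% under the gate and 14–20% under B–D as nulls.

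*Endpoint-wise reading (alternatives), real effect on 6 mg peak only, carried endpoint at unadjusted 5%:* error is 6.4–7.1% at 80% power and 9.2–9.6% at a z-shift of 6. The second range is plausible on its face. Once 6 mg peak is certain to reject, two true nulls (6 mg AUC and 1.5 mg peak) are each tested at 5%, and independence would give 1 − 0.95² = 9.75%. Under the global null this reading stays at 3.7–4.8%.

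**The case against.** The strongest reply is that the inversion depends on a figure that could not be seen. SAP 6.11 labels the null H_0, so H_1 and H_2 may well be alternatives. Sentences B and C then agree with the gate and with the stated dose order. Figure 1 may also define the intersection test and the adjustment, so an analyst who has it may face less doubt than the text suggests. This stands as a limit on the inversion, and on the 6.7–8.8% and 14–20% figures that depend on it. It does not rescue sentence D, which lets 1.5 mg be tested after a single 6 mg success. No definition of H_1 and H_2 reconciles that with the both-endpoints requirement.

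A second fair point is that sentence E speaks of adjusted p-values, while the endpoint-wise error figures above use an unadjusted 5% test. With the within-dose adjusted 1.5 mg p-value they fall to 5.3–5.8% at 80% power and 7.4–7.9% at a z-shift of 6. The inflation is smaller but still present.

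Third, endpoint-wise progression with a suitable alpha allocation would be a legitimate design, and sentence D may hint that it was meant. That is true, but SAP 6.15 specifies no such allocation and sentence A says otherwise.

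Finally, this is a single-centre Phase II trial with 24 evaluable patients, and the 6 mg tests are unaffected. That limits the consequence. It does not excuse the text, because the SAP itself undertakes to control the overall error.

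**Conclusion.** The concern holds. SAP 6.15 contains two incompatible decision rules, and nothing in SAP 6.11, Protocol 10.3.1, the Protocol synopsis or SAP 6.19 resolves them. The conflict between the gate and the single-endpoint sentence is certain on every reading examined. The full inversion, stopping on success and proceeding on failure, applies if H_1 and H_2 are nulls, which is the ordinary sense of the words and fits SAP 6.1. No reading examined satisfies every sentence and also allows 1.5 mg to be declared.

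On the null reading without carry-down, the error under the global null rises from 3.7–4.8% to 6.7–8.8%, and the chance of a 1.5 mg claim falls from 62–65% to 14–20% when all four comparisons have 80% power. These sizes rest on the assumed peak–AUC correlation, the assumed Holm or Hochberg test and the assumed power at 1.5 mg. The contradiction itself rests on none of them. It must be fixed before unblinding.

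**What to change.** Before unblinding, amend SAP 6.15 as follows.

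1. Define H_1 and H_2 as the 6 mg null hypotheses for peak FEV1 and AUC0-12h FEV1.
2. Keep the both-endpoints gate and delete sentences B, C and D. In their place write: *If both H_1 and H_2 for 6 mg are rejected, the same procedure is applied to 1.5 mg versus placebo; if either is not rejected, confirmatory testing stops and the 1.5 mg results are descriptive.*
3. Name the within-dose intersection test and say how the adjusted p-value is computed.
4. Check that Figure 1 shows the same rule.

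This keeps the SAP's own gate and the dose order in both documents. If endpoint-wise progression was intended instead, the gate sentence has to go and an alpha allocation that controls the overall error has to be written in.

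The cost is SAP wording only. Data, estimates, confidence intervals and sample size do not change.

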6.16 Spirometry: Pulmonary Function Tests

Spirometry (FEV₁ and FVC) will be performed at screening, the end of study visit and the following time points in each treatment period:

• Day 1: pre-dose; 5, 15 and 30 minutes and 1, 1.5, 2, 4, 6, 8 and 12 hours

• Day 2: pre-dose; 15 and 30 minutes and 1, 2, 3 and 4 hours

• Day 3: pre-dose; 5, 15 and 30 minutes and 1, 1.5, 2, 4, 6, 8, 12, 15 and 24 hours Post-dose measurements will be taken in relation to the morning dose of tiotropium DPI and RPL554 or placebo. The 12-hour measurement will therefore be taken predose before the evening dose of RPL554 or placebo. The 24-hour measurement on Day 3 will be taken in the morning on Day 4 prior to discharge from the study centre.

Spirometry assessments will be made in accordance with ATS/ERS guidelines (Miller et al, 2005). At all timepoints, three technically acceptable measurements should be made and recorded. Spirometry assessments may be performed up to eight times to obtain three acceptable readings according to ATS guidelines (Miller, 2005). The highest FEV₁ and FVC readings from each assessment will be used for analysis even if the FEV₁ and FVC values come from two different forced exhalations.

Pulmonary function tests data (FEV $_1$ and FVC) including change from baseline will be listed and summarised.

Mean (±Standard error of mean (SEM)) figures will be presented for FEV_1 and FVC data separately using change from baseline data where baseline is the pre-dose Day 1 value. Separate figures will be generated for FEV_1 and FVC data collected from Day 1 to Day 3. The three treatments will be represented on the figures using different colours.

6.17 Pharmacokinetics

Plasma concentrations of RPL554 will be listed and summarised over time. Values below the lower limit of quantification (LLOQ) of 5 pg/mL will be set to 0.5 *LLOQ for calculation of summary plasma concentration statistics. Individual plasma concentration profiles will be plotted both on the original scale and on the log scale separately. Mean (±SD) and median plasma concentration profiles will be plotted on the original scale and on the log scale.

The following steady state pharmacokinetic parameters will be calculated from plasma concentrations of RPL554 using standard non-compartmental methods by LGC Ltd and transferred to SQN for analysis.

- Area under the plasma drug concentration versus time curve (AUC) up to 12 hours (AUC_{0-12h} (pg.h/mL))
- Area under the plasma drug concentration versus time curve (AUC) up to 24 hours (AUC_{0-24h} (pg.h/mL))
- Area under the plasma drug concentration versus time curve (AUC) up to the last measurable time point (AUC_{0-t} (pg.h/mL))
- Maximum plasma drug concentration (C_{max} (pg/mL))
- Time of observed maximum plasma drug concentrations (t_{max} (h))
- The first-order apparent elimination rate constant (K_{el} (hr⁻¹))
- Half-life (t_{1/2}(h)) The apparent clearance (CL/F (mL/min))
- The (apparent) volume of distribution (V_z/F (L))

These PK parameters will be summarised by treatment using descriptive statistics (n, geometric mean, coefficient of variation (CV), minimum, maximum and median for AUC parameters, C_{max} , half-life, and n, arithmetic mean, standard deviation, minimum, maximum and median for.: $t_{1/2}$, t_{max} , C_{max} , AUC_{0-12h} , AUC_{0-24h} and AUC_{0-t} , CL/F, V_z/F . K_{el} .

The PK parameters will be listed.

6.18 SAFETY EVALUATION

Safety and tolerability will be assessed by assessments including physical examinations, vital signs, 12-lead ECGs, 24-Hour Holter monitoring, adverse event recording and laboratory safety tests.

Safety data will be summarised by treatment group and time point of collection when appropriate. For continuous variables, the change from baseline (pre-dose at each treatment day) to each post-dose time point will also be calculated and summarised. Data will further be illustrated by shift tables (showing changes from low/normal/high)

and shift plots for selected time points. Separate listings will be generated of abnormal values occurring after the first dose of study treatment.

